#### **1.0 INTRODUCTION**

Every year several million women worldwide acquire an abdominal scar as a result of caesarean delivery. Obstetricians often consider skin closure after a caesarean section as a trivial aspect of the procedure, because the skin scar is deemed the normal and inevitable price we pay foe tissue repair. Moreover, the anatomical location of caesarean scars, which hide easily beneath underwear, and the generally held belief that all transverse suprapubic incision heal about equally well further contribute to the underestimation by practitioners of the importance of scar appearance to patients.

Young women place supreme importance on cosmetic outcomes, but scarring can also affect patient in term of symptoms ( pain, tenderness, and itching ) and has the potential to have a negative impact overall quality of life, being a source of considerable distress, loss of self esteem and stigmatization.

The final appearance and the function of the healed skin is dependent on patient and wound factors, which are often outside the control of a surgeon, and technical factors, which are completely within the control of the surgeon and include closure material and technique of skin apposition.

There were few study trial done with the aims of preventing hyperthropic scar formation following caesarean section. Antonella Cromi et al (obstet Gynaecol 2010, 203: 36.el-8) did a randomized trial on 123 patient to compare scar quality associated with different types of wound closure method after caesarean section. The result showed that the were no difference in scar quality in either staples or 3 different types of subcurticular sutures.

Atkinson et al (2005 American Society of plastic surgeon) performed a randomized controlled trial involving 70 patient to determine the efficacy of paper tape in preventing hyperthrophic scar formation in surgical incisions that traverse Langer's skin tension lines.

Result suggest that tension acting on a scar is the trigger for hyperthrophic scarring, and paper tape is likely to be an effective modality for prevention of hypertrophic scarring through its ability to eliminate scar tension.

The aims of this study is to prevent hypertrophic scar and keloid formation post caesarean section using PROTESCAL adhesion barrier. PROTESCAL, a combination of hyaluronic acid, methylcellulose, and alginate was manufactured by Korean pharmaceutical companies and became available since 2012. PROTESCAL was developed to prevent complications such as ileus, pain and infertility due to postoperative adhesion.

Hyaluronic acid is a natural polymer of disaccharides, one of the components of the extracellular matrix. It is present in the skin, cartilage, bone and brain. Because of its biocompatibility, moisture capacity, and viscoelasticity, hyaluronic acid has been used as

artificial tears in drug delivery systems, and tissue restoration materials, and it plays a role in inflammation, granulation and re-epithelization for wound healing. It has proved valuable in neurosurgery and dermatology because hyaluronic acid and degradation products can modulate wound healing. There is wide scientific evidence on the positive role of hyaluronic acid in tissue regeneration and wound healing.

Carboxymethylcellulose is a high molecular weight polysaccharide that has a concentration and volume that are inversely correlated with its antiadhesive agent. The combination of carboxymethylcellulose and hyaluronic acid has had a preventive effect on the formation of adhesion in various surgical fields.

Alginate has been used as a wound dressing agent, its calcium or sodium form has hemostatic and antimicrobial effects, and it has been shown to prevent adhesion formation in animal studies.

With the combination of hyluronic acid, methylcellulose and alginate, which already proven scientifically benefit in wound healing, we aims to prevent the hypertrophic scar and keloid formation following caesarean section by applying PROTESCAL in subcutaneous layer prior to skin closure.

# 2.0 OBJECTIVE OF THE STUDY

#### 2.1 General Objective

To evaluate the effectiveness of Protescal in preventing post caesarean section hypertrophic scar and keloid and pelvic adhesion.

# **2.2 Specific Objectives**

To determine the effectiveness of Protescal in preventing hypertrophic scar and keloid compared to control group.

To determine the effectiveness of Protescal in preventing pelvic adhesion

# **3.0 OUTCOMES**

#### 3.1 Primary

To assess the outcome of healing of the external scar

#### 3.2 Secondary

To look for adhesion formed during next caesarean section

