# 4.0 RESEARCH METHODOLOGY

#### 4.1 Study design

Prospective, randomized controlled clinical trial

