#### 4.3 Study Population

All women undergoing elective caesarean section, without any history of previous abdominal surgery; who planned for further pregnancy and consented to participate in this study.

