#### 4.4 Duration of study

6 months duration; from April 2017 to October 2017

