#### 4.8 Data Collection And Statistical Analysis

SPSS (Statistical Package of Social Science) version 20.0 will be employed proportional data will be compared with chi square. The Fisher exact test will be chosen if the expected size of any cell of the contingency table is less than 5. Continuous data will be compared using the Wilcoxon rank-sum test. Multiple logistic regressions will be use to model the relationship between group assignment, controlling for possible confounders. P<0.05 will be considered significant.

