**Cohen's Sample Size Table** 

# 4.10 Study Flow Chart

 $\downarrow$ 

Protescal applied at uterine suture site and in subcutaneous tissue layer prior to skin closure

No protescal applied at uterine suture site and in subcutaneous tissue layer prior to skin closure

After delivering the baby through caesarean section, uterine muscle is closed in 2 layers with braided absorbable suture, polyglactin 910 (vicryl no 1).

After haemostasis secure, 4 ml Protescal gel apply at the uterine suture site.

Peritoneal layer close using braided absorbable suture, polyglactin 910 (vicryl no 1).

Rectus sheath suture using braided absorbable suture, polyglactin 910 (vicryl no 1).

Subcutaneous tissue close interruptedly using braided absorbable suture, polyglactin 910 (vicryl no 1).

1 ml Protescal gel apply in subcutaneous tissue prior to skin closure.

Skin close with subcuticular method using braided absorbable suture, polyglactin 910 (vicryl 3-0).

Wound healing assess on 10th day post caesarean section using REEDA scale, which had criteria including redness, edema, ecchymosis, discharge and approximation.

On 3rd month, the degree of scarring assess using the Vancouver scar scale including pigmentation, height, pliability and vascularity.

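### Adhesion is seen only in women who conceive again and have another caesarean, so the planned adhesion comparison cannot carry a claim of effectiveness for the women randomised

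*Combined protocol and SAP*

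**What the plan says.** Section 4.1 describes the study as a "Prospective, randomized controlled clinical trial". The second specific objective in 2.2 is causal: "To determine the effectiveness of Protescal in preventing pelvic adhesion". Section 2.1 includes the same aim. The flow chart in 4.10 gives the gel at the uterine closure in one arm ("After haemostasis secure, 4 ml Protescal gel apply at the uterine suture site") and none in the other.

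The only observation of adhesion is the secondary outcome in 3.2: "To look for adhesion formed during next caesarean section". Section 4.3 restricts entry to women "who planned for further pregnancy and consented to participate in this study". The introduction explains the product's purpose: "PROTESCAL was developed to prevent complications such as ileus, pain and infertility due to postoperative adhesion".

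Section 4.8 assigns no test to adhesion by name. It says that "proportional data will be compared with chi square", with Fisher's exact test for small expected counts, and adds multiple logistic regression with adjustment for possible confounders. It does not say how women without a repeat caesarean enter the analysis. Section 4.4 gives "6 months duration; from April 2017 to October 2017", and the last assessment described in 4.10 is the scar score at month 3.

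**The concern.** The objective concerns all the women randomised, but the outcome exists only for those who later reach a repeat caesarean. Conceiving, carrying the pregnancy and being delivered by caesarean all happen after the gel is given or withheld. By the protocol's own account adhesion can cause infertility, so women with worse adhesions may be less likely to be assessed. If the gel reduces adhesion, it also changes who is assessed, and the two observed groups are no longer the groups that randomisation made comparable.

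At stake is one of the two specific objectives. An analyst applying 4.8 to the women assessed would obtain a p-value that looks randomised but answers a question about a selected subset. Extending follow-up is the natural repair for the short study period. It would supply more such data without removing the selection, because a woman whom adhesion prevents from conceiving is never observed.

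**Working it through.** **The plan's own figure.** Section 4.9 states 45 per group for a standardised difference of 0.60, alpha 0.05 and power 0.80. The normal approximation gives 2 × (1.960 + 0.842)² / 0.60² = 43.6, so 44. The exact t calculation gives 45. The figure reproduces, but it concerns a difference in means. The documents contain no calculation, adhesion risk, severity distribution or repeat-caesarean rate for the adhesion outcome. Everything below except the 45 is therefore an assumption.

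**Formula.** Let p be the true proportion in each adhesion state within an arm, and r the chance of being assessed at a repeat caesarean in that state. The observed proportion in a state is p × r divided by the sum of p × r over the states.

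**Assumed states (none / moderate / severe).** Control 50/30/20%, gel 60/30/10%. The true contrasts (control minus gel, or gel against control) are:
- Any adhesion 50% v 40%: difference 10 points, odds ratio (0.40/0.60)/(0.50/0.50) = 0.67.
- Severe 20% v 10%: difference 10 points, odds ratio (0.10/0.90)/(0.20/0.80) = 0.44.

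**Worked example, assessment chances 50/45/20%.**
- Control: 0.250 + 0.135 + 0.040 = 0.425, or 19.1 of 45 assessed.
- Gel: 0.300 + 0.135 + 0.020 = 0.455, or 20.5 of 45 assessed.
- Any adhesion: 0.175/0.425 = 41.2% v 0.155/0.455 = 34.1%.
- Severe: 0.040/0.425 = 9.4% v 0.020/0.455 = 4.4%.

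**Three assessment patterns.**

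| Chance assessed | Women assessed of 45 (control, gel) | Severe, control v gel | Severe difference | Severe OR | Any-adhesion OR |
|---|---|---|---|---|---|
| All women | 45, 45 | 20% v 10% | 10 points | 0.44 | 0.67 |
| 50/45/20% | 19.1, 20.5 | 9.4% v 4.4% | 5.0 points | 0.44 | 0.74 |
| 70/60/20% | 25.7, 27.9 | 7.0% v 3.2% | 3.8 points | 0.44 | 0.76 |
| 40/40/10% | 15.3, 16.7 | 5.9% v 2.7% | 3.2 points | 0.44 | 0.77 |

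**A two-state check.** Take true adhesion risks of 40% v 20%, and let adhesion multiply the chance of assessment by k in both arms. The observed risk is pk/(pk + 1 − p). For k = 0.75, 0.5 and 0.25 the observed risks are 33 v 16%, 25 v 11% and 14 v 6%. The differences are 17.5, 13.9 and 8.4 points against a true 20. The odds ratio stays at 0.375 throughout.

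**The direction is not guaranteed.** Take control 60/20/20% and gel 65/30/5% (none/mild/severe), with assessment chances 50/40/10%. The true any-adhesion risks are 40% v 35% (odds ratio 0.81). The observed risks are 0.10/0.40 = 25.0% v 0.125/0.45 = 27.8% (odds ratio 1.15), so the sign reverses.

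**How little the assessed women settle.** In the worked example 17.5% of all control women and 15.5% of all gel women are seen to have adhesions, while 57.5% and 54.5% are not assessed. Assigning every unassessed woman either way puts the control risk between 17.5% and 75%, and the gel risk between 15.5% and 70%. With opposite assignments, the difference (control minus gel) lies between 17.5 − 70 = −52.5 and 75 − 15.5 = +59.5 points.

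**The case against.** The best counter-argument is that the apparent damage depends on the scale. The regression in 4.8 yields odds ratios, and in all three patterns the severe-adhesion odds ratio is essentially unchanged; its risk ratio moves only from 0.50 to 0.46–0.47. Assessment also differs little by arm: 42.5% v 45.5% in the worked example, or about 1.4 women of 45. This stands. A reader who looks only at the risk difference might infer that much of any benefit must vanish, and the documents do not support that. It does not rescue the plan, however. The odds ratio is preserved only when assessment depends on a yes/no state and equally in both arms. It moves for any adhesion once severity matters, and 3.2 and 4.8 name no effect measure for adhesion.

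Second, a reader might infer that a positive adhesion result would be worthless or that the test is invalid in every case. That is too strong. If the gel affects neither adhesion nor conception, selection is equal in both arms and the test keeps its error rate. The most plausible bias also runs towards no difference, which weakens a null finding more than a positive one.

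Third, the introduction states why the product was developed. It gives no strength for the link between adhesion at a caesarean closure and later conception, so the size of the selection is unknown. This also stands. So does the point that the smaller number assessed is a loss of precision, separate from selection.

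Fourth, 4.3 admits only women planning another pregnancy, and 4.8 includes confounder adjustment. The first reduces non-assessment by choice, but not through infertility or vaginal birth. The second cannot recover outcomes that were never observed.

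Finally, with a 6-month study and a last described assessment at month 3, almost no repeat caesarean could be seen. That is a separate problem, and solving it would leave this one.

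**Conclusion.** The concern holds as a limit on what the adhesion outcome can show. Assessment depends on a post-randomisation event that the protocol itself links to adhesion, the gel is meant to change adhesion, and nothing in the plan accounts for the women not assessed. If the gel has an effect, the comparison among assessed women does not estimate effectiveness in the women randomised.

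The size cannot be derived from the documents. Under the assumed figures the severe-adhesion risk difference falls from 10 to about 3–5 points while its odds ratio stays near 0.44, and the any-adhesion odds ratio moves from 0.67 to about 0.74–0.77. Attenuation is the most plausible direction, though other assumptions can reverse the sign. A finding of no difference would be the least trustworthy result. This touches a secondary outcome, but one that serves a stated specific objective, so it should be corrected.

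**What to change.** 1. In 2.1 and 2.2, reword the adhesion aim as describing the adhesions found among randomised women who have a repeat caesarean. In 4.8, label any between-arm test of adhesion as exploratory and not evidence of effectiveness.
2. In 4.8, add a table by arm, with all randomised women as denominator. It should show how many had a repeat caesarean with adhesions assessed and how many did not, with the reason where known: not pregnant, vaginal birth, delivered elsewhere, or no contact.
3. Optionally, if adhesion is compared between arms, give bounds that assign every unassessed woman in each arm, including opposite assignments between arms. Assigning only women who were trying without conceiving would leave the others unaccounted for. The bounds will probably be wide, which is itself informative.

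The cost is a few sentences, one table and a more modest adhesion claim. Collecting reasons needs some contact after the month-3 visit, which the plan does not describe, so this is new work. No extra women or procedures are required. The 6-month duration in 4.4 needs its own correction.

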#### 4.6 Exclusion Criteria

Patient who are allergic to protescal Patient with previous abdominal surgery Patient with surgery complication

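### No safety outcome or adverse-event recording is planned for gel placed at two sites, and an undated complication exclusion can remove women after allocation

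*Combined protocol and SAP*

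**What the plan says.** **Outcomes and analysis.** Section 3.1 gives the primary outcome as "To assess the outcome of healing of the external scar", and section 3.2 gives the only secondary outcome as "To look for adhesion formed during next caesarean section". The objectives (2.1 and 2.2) concern effectiveness alone. Section 4.8 describes tests for proportions and continuous data and a logistic model. It mentions no adverse events and no analysis population.

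**Product and exposure.** The introduction states that "PROTESCAL was developed to prevent complications such as ileus, pain and infertility due to postoperative adhesion". The flow chart (4.10) uses the gel at two sites: "4 ml Protescal gel apply at the uterine suture site" and "1 ml Protescal gel apply in subcutaneous tissue prior to skin closure".

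**Assessments.** The flow chart plans two: "Wound healing assess on 10th day post caesarean section using REEDA scale, which had criteria including redness, edema, ecchymosis, discharge and approximation", and the Vancouver scar scale at month 3, with pigmentation, height, pliability and vascularity. Neither is restricted to one arm.

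**Exclusion and allocation.** Section 4.6 excludes a "Patient with surgery complication", with no definition and no timing. Section 4.7 names the operating theatre or the antenatal clinic as the place of randomisation.

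**The concern.** There are two separate gaps.

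1. **Harm is not counted.** The gel was developed against adhesions and is here also put into the subcutaneous layer of a fresh wound. The introduction argues only for benefit in that layer. A trial that reports effectiveness with no planned count of complications gives the reader nothing to set against the benefit.

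2. **The complication rule can act after allocation.** A woman randomised in clinic has not yet had her caesarean, so any complication of it comes after allocation. If she is then excluded, the arms compared are no longer the arms randomised. If the gel raises the complication rate and complications worsen scars, the women removed are disproportionately poor results from the gel arm. That would touch the primary outcome as well as safety reporting.

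**Working it through.** **Step 1: the plan's own figure.** Section 4.9 uses an effect size of 0.60, alpha 0.05 and power 0.80, and arrives at 45 per group. Reading 0.60 as Cohen's d (as the section's formula and table do) with a two-sided test:

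n = 2 × (1.96 + 0.84)² / 0.60² ≈ 43.6, so 44 by the normal approximation.

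The exact t calculation gives power 0.795 at 44 and 0.804 at 45. The stated 45 reproduces and is used below.

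**Step 2: which harms each planned assessment would show.**

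| Item | Day-10 REEDA | Month-3 Vancouver scale | Adhesion at next caesarean |
|---|---|---|---|
| Redness, oedema, bruising, discharge, gaping | Yes, as healing items | No | No |
| Diagnosed infection, collection, dehiscence as events | No | No | No |
| Readmission or re-intervention | No | No | No |
| Early harm at the uterine site | No | No | No |

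Adhesion at a later operation concerns the pelvis, but it is an effectiveness outcome.

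**Step 3: timing of the exclusion.** Section 4.6 already has a separate line for previous abdominal surgery, and 4.3 and 4.5 repeat it. The complication line therefore adds little unless it refers to the present caesarean. For a woman randomised in clinic, such a complication can only follow allocation. No section says that all randomised women are analysed.

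**Step 4: what 45 per arm could show if harm were counted.** The documents give no event rates, so all rates here are assumptions.

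- Expected events per arm, 45 × p: 0.9 at 2%, 2.25 at 5%, 4.5 at 10%, 9 at 20%.
- Chance of at least one event in an arm, 1 − (1 − p)^45: 36% at 1%, 60% at 2%, 90% at 5%, 99% at 10%.
- Upper limit after 0 of 45, two-sided exact 95%: 1 − 0.025^(1/45) = 0.079, that is 7.9%.

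| Assumed rates, control vs gel | Power at 45 per arm, exact Fisher | n per arm for 80% power (normal approximation) |
|---|---|---|
| 2% vs 4% | 0.4% | 1141 |
| 5% vs 10% | 6% | 435 |
| 10% vs 20% | 18% | 199 |
| 5% vs 20% | 48% | 76 |

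**Step 5: size of the possible bias in the scar comparison.** Suppose a complication worsens the scar score by δ standard deviations in either arm, and every affected woman is removed. An arm's full mean is m + pδ, and after removal it is m. The comparison then shifts in favour of the gel by (p_gel − p_control) × δ. With 10% and 5% the shift is 0.05δ; with 20% and 5% it is 0.15δ. To equal the planning effect of 0.60, δ would have to be 0.60/0.05 = 12 SD or 0.60/0.15 = 4 SD. At these rates, removal could distort the scar result but could not by itself produce the planned effect.

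**The case against.** The strongest reply is that the trial is not blind to wound harm. REEDA at day 10 includes discharge and approximation, appears to apply to both arms, and plausibly falls within the primary outcome of scar healing. This stands. A reader might infer that wound harm would go wholly unseen, and the documents do not support that. What remains missing is any count of complications as events, any harm analysis, any wound record after day 10 beyond scar appearance, and any cover of the uterine site.

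The second reply is that the complication line sits among eligibility criteria and may mean an operative complication arising before the gel is applied, in which case it hides no gel-related event. This also stands as a possible reading. A reader might infer that the rule, as written, deletes harm events. The text does not say so; it leaves the timing open. The wording of 4.7 is loose too, since the place named could be where the sequence is generated and not where each woman is allocated. The top of the flow chart in 4.10 was not legible in the text available and may show when exclusions are made. None of this removes the problem: a rule without timing permits exclusion after allocation, and nothing in the text available prevents it.

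Third, 45 per arm is too few to detect plausible differences in harm. This is correct, and it is why the proposed reporting is descriptive. It is not a reason to leave events unrecorded.

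**Conclusion.** The point holds in this form: no safety outcome, adverse-event recording or harm analysis is specified for a gel used at two sites, and the undated complication criterion can remove women after allocation.

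The reporting gap does not depend on any assumed rate. The bias depends on three conditions: that the criterion is applied after allocation, that the gel raises complications, and that complications worsen scar scores. Under the assumed rates it is 0.05 to 0.15 SD per SD of worsening, so modest against the planning effect of 0.60. The loss of safety information is the larger matter.

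A reader might also infer that the sponsor intends to recommend the gel as safe. The plan makes no such claim; its objectives are confined to effectiveness. The change should be made, but the omission does not by itself invalidate the scar comparison.

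**What to change.** - **Section 3.2:** add a secondary safety outcome consisting of wound infection, seroma or haematoma, dehiscence, readmission, re-intervention, and any other postoperative adverse event, including those related to the uterine site. Record it at the existing day-10 and month-3 assessments for every randomised woman.
- **Section 4.8:** report counts by allocated arm with a risk difference and an exact 95% confidence interval, and name the interval method. State that this is descriptive and that few or no events would not establish safety. Show the REEDA discharge and approximation items by arm, apart from the total.
- **Section 4.6:** define the complication criterion and state that it applies only to eligibility before randomisation. For women randomised in clinic it will then exclude nobody on account of the present operation, which is the intended effect.
- **Analysis population:** state that women with a complication after allocation are followed and analysed in their allocated arm.

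The cost is a few lines on forms used at existing assessments and one extra table. The downside is wide intervals that will not prove safety.
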